5.7.4. Other Significant AEs

CNS Hemorrhage, Seizures, falls, and hypersensitivity reactions are considered significant AEs and are being monitored in this study. As listed in Table 6, CNS hemorrhage, seizures, hypersensitivity, and fall events will be summarized by safety analysis groups and will be listed.

CNS hemorrhage events will be identified by the eCRF and by using a standardized MedDRA query (SMQ), consisting of selected preferred terms within SMQ of "Haemorrhagic central nervous system vascular conditions" (narrow and broad scope). The SMQ list of PTs may be modified based on newer version of MedDRA when available and safety team's discretion. All CNS hemorrhage events will be summarized by preferred term. A separate summary table will be presented with all hemorrhagic CNS vascular conditions except subdural hematomas.

Seizure events will be identified using the SMQ of "Convulsions" (narrow and broad scope). ARIA status of subjects with seizure will be presented, splitting by the number of subjects with non-evaluable ARIA status (no post-baseline MRI), subjects with no ARIA event during the study and subjects who experienced ARIA during the study.

Hypersensitivity events will be identified using the SMQ of hypersensitivity (narrow and broad scope), SMQ of angioedema (narrow and broad scope) and SMQ of anaphylactic reaction (narrow and broad scope). The SMQ list of PTs may change due to the newer version of MedDRA and at the safety team's discretion.

Fall events will be identified based on the preferred term "Fall" and number of falls will be presented.

Table 6 List of Planned Analyses for ARIA and Other Significant AEs

Analysis	Repeat stratified by ?	Repeat by Core Treatment Period?
Incidence of ARIA events by previous ARIA-E experience	Yes	Yes
Maximum MRI severity and worst symptomatic status of ARIA events	Yes	Yes
Maximum MRI severity and worst symptomatic status of ARIA events among participants with ARIA	No	Yes
Onset of ARIA events	No	Yes

Product: Aducanumab

Statistical Analysis Plan

Study: 221AD304 Version: 2.0

Analysis	Repeat stratified by ?	Repeat by Core Treatment Period?
Resolution of ARIA-E and stabilization of ARIA-H	No	Yes
Summary of first ARIA-E	No	Yes
Recurrent ARIA-E	No	Yes
ARIA-related adverse events by SOC/PT	No	Yes
Summary of symptomatic ARIA	No	Yes
Summary of serious and severe ARIA and symptoms	No	Yes
Serious or severe ARIA-related adverse events by PT	No	Yes
Summary of ARIA-H events by ARIA-E status	No	Yes
Haemorrhagic CNS vascular conditions events ¹²	No	No
Haemorrhagic CNS vascular conditions events excluding subdural hematomas 12	No	No
Hypersensitivity events ¹³	No	Yes
Serious hypersensitivity events ¹³	No	Yes
Related hypersensitivity events ¹³	No	Yes
Seizures ¹⁴	No	Yes

Study: 221AD304 Version: 2.0

Analysis	Repeat stratified by ?	Repeat by Core Treatment Period?
Fall ¹⁵	No	Yes

On safety population.

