#### Long-Term Extension Period Results

Data from the LTE of Study 221AD103 also provide insights relevant for the study population targeted in the present study (Study 221AD304). In the LTE period, those participants who started on active treatment at the beginning of the placebo-controlled period continued treatment (at the same dose as in the placebo-controlled period, except for the 1 mg/kg cohort who were switched to 3 mg/kg), while participants from the placebo arms initiated dosing with aducanumab. The main findings in Study 221AD103 during the LTE period regarding efficacy and safety for the high-dose groups (fixed-dose regimen of 10 mg/kg and titration to 10 mg/kg, which are the 2 relevant groups regarding the target dose in Study 221AD304) were the following:

- At Week 222, the adjusted mean changes from baseline in the 10 mg/kg fixed-dose and 10 mg/kg titration groups (3.83 and 3.68, respectively) were numerically smaller than the adjusted mean changes in the 1, 3, and 6 mg/kg groups that continued dosing (range 5.48 to 8.43) and the group that switched from placebo to aducanumab after 1 year (6.15).
- 2. The safety profile of aducanumab in the LTE was similar to that seen in the placebo-controlled period:
  - Participants who began treatment with aducanumab during the placebo-controlled period had a low incidence of ARIA-E in the LTE (5% for 10 mg/kg fixed dose and 17% for titration to 10 mg/kg).

The incidence of ARIA-E in participants who began treatment with aducanumab in the LTE (22%) was similar to the incidence in participants who began treatment in the placebo-controlled period (24%).

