#### 5.4. Benefit-Risk Assessment

There are currently no available therapies that modify the clinical course of Alzheimer's disease. Analyses of data collected through the end of the study (Study 221AD301 database lock on 15 November 2019 and Study 221AD302 database lock on 13 November 2019, with efficacy data after 20 March 2019 censored) in the 2 Phase 3 aducanumab clinical studies showed that, in Study 221AD302, treatment with aducanumab significantly reduced clinical decline in patients with early Alzheimer's disease as measured by the prespecified primary endpoint (CDR-SB) and by the 3 secondary endpoints (MMSE, ADCS-ADL-MCI, and ADAS-Cog 13) in the high-dose group. In addition, Study 221AD301 contained supportive data, based on post-hoc analyses of subsets of participants who received sufficient exposure to the highest dose (10 mg/kg) of aducanumab. Additionally, data from the Study 221AD103 of aducanumab, with up to 4 years of FU data on treatment, suggested a continued benefit on the rate of clinical decline with continued aducanumab treatment (changes from baseline in the groups that received either 10 mg/kg fixed dose or 10 mg/kg titration since the beginning of the study were numerically smaller than those in the groups that switched from placebo to aducanumab).

[figure not shown]
As of 04 May 2020, a total of 3078 participants have been exposed to aducanumab across completed or terminated clinical studies (including 3050 participants with Alzheimer's disease and 28 healthy volunteers). Of those, 2757 participants were enrolled in the Phase 3, placebo-controlled studies (Studies 221AD301 and 221AD302) for approximately 3983.5 person-years of exposure and totaling 4736.1 person-years of FU. The most frequent AE, among participants from Studies 221AD301 and 221AD302 with a target dose of 10 mg/kg, was ARIA-E (35.4%). The majority of participants with ARIA-E were asymptomatic, and participants with symptomatic ARIA-E had symptoms that were predominantly mild or moderate in clinical severity. Symptoms reported during ARIA-E episodes included headache, confusional state, dizziness, fatigue, nausea, or rarely seizures, including prolonged seizures.. In the majority

[figure not shown]

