of participants with ARIA-E, the first ARIA-E events were documented to have fully resolved (800 of 815 participants [98.2%]). In the clinical studies, some participants with an initial episode of ARIA-E that resolved subsequently experienced a second, later episode of ARIA-E. This was referred to as "recurrent ARIA-E" in the clinical studies. Recurrent ARIA-E events were less likely to be symptomatic than first ARIA-E events (recurrent: 13.1% versus first: 23.6%). As with first ARIA-E events, in nearly all participants with second ARIA-E events, the events resolved during the study (231 of the 236 participants [97.9%] with second ARIA-E), and in the majority of participants with resolved second events, ARIA-E resolved within 12 weeks. Other frequent AEs, among participants from Studies 221AD301 and 221AD302 with a target dose of 10 mg/kg, included headache (20.5%), ARIA-H micro-hemorrhage (19.1%), fall (15.0%), nasopharyngitis (14.5%), and ARIA-H superficial siderosis (14.6%). Similar to ARIA-E, the majority of participants with ARIA-H micro-hemorrhage and ARIA-H superficial siderosis were asymptomatic. Notably, transient treatment interruption has been routinely implemented in all aducanumab studies for participants with ARIA events meeting certain criteria. Resumption of dosing after this treatment-free period was not associated with an increased incidence of AEs or immunogenicity.

The benefit-risk profile of aducanumab is considered positive for investigational use in both treatment-naïve participants as well as in previously treated participants who have had a treatment-free period.

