# 16.7. Sample Size Considerations

Given that the study population depends on the feeder studies, no sample size was determined for this study.

At the time that the feeder studies were stopped in March 2019, approximately 2600 participants had received treatment in 1 of those feeder studies. Approximately 400 participants were on placebo ("aducanumab treatment-naïve participants") and approximately 2200 participants had received aducanumab ("aducanumab previously treated participants"). Biogen estimates that of these 2600 participants, 2400 participants could be eligible based on inclusion and exclusion criteria to participate in the current study.

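### The seizure table classifies participants by ARIA at any time in the study, so part of the overlap it shows is chance, equal in size to the any-ARIA incidence; a split by timing is a cheap improvement

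*SAP*

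**What the plan says.** SAP 5.7.4 names seizure as one of four significant adverse events, found through the Convulsions MedDRA query, summarised by safety analysis group and listed. It then says that "ARIA status of subjects with seizure will be presented, splitting by the number of subjects with non-evaluable ARIA status" (defined as having no post-baseline MRI), "subjects with no ARIA event during the study and subjects who experienced ARIA during the study". It gives no window or order relative to seizure onset, and does not separate ARIA-E from ARIA-H.

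The timing information exists elsewhere in the plan:

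- SAP 5.7.3.1 dates each ARIA event from the detecting MRI to the MRI showing resolution (ARIA-E) or stability (ARIA-H). It calls an ARIA-E and an ARIA-H event concurrent when these durations overlap.
- The AE listing in SAP 5.7.2.2 carries onset and end dates and an investigator flag for whether the event is a symptom of ARIA.
- SAP 5.7.3.2 plans a table and a listing of AEs that the investigator considers related to ARIA.

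**The concern.** Protocol 5.4 includes seizures, described as rare, among the symptoms reported during ARIA-E episodes. A table of seizure participants by ARIA status will therefore be read as evidence on whether seizures accompany ARIA. Under the stated rule, three very different histories share one cell: a seizure during ARIA-E, a seizure a year after ARIA-E resolved, and a seizure long before any ARIA. One asymptomatic micro-hemorrhage at any visit also puts a participant there.

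The study has a single arm, so no comparator shows how much of the overlap is coincidence. Previously treated and treatment-naïve participants may also differ in ARIA incidence. The ARIA share among seizure participants could then differ between the safety analysis groups with no difference in any seizure–ARIA link.

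**Working it through.** The plan states no expected overlap and no ARIA rate for 221AD304, so there is no figure to reproduce. The check bounds the chance overlap under each rule.

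**Inputs**

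- Feeder pool (Protocol 16.7): "Approximately 400 participants were on placebo" and about 2200 had received aducanumab, of about 2600. Shares: 400/2600 = 15.4% and 2200/2600 = 84.6%. The SAP reports 1696 enrolled but not their split by prior exposure, so using these weights is an assumption.
- 221AD103 extension (Protocol 5.1.2): participants treated from the start "had a low incidence of ARIA-E in the LTE (5% for 10 mg/kg fixed dose and 17% for titration to 10 mg/kg"; those first treated in the extension had 22%.
- Phase 3, 10 mg/kg target dose (Protocol 5.4): ARIA-E 35.4%, micro-hemorrhage 19.1%, superficial siderosis 14.6%.
- Follow-up from first dose: 118 weeks without the LTE; 152 + 18 = 170 weeks with it, as planned.
- ARIA-E episode length: 12 to 20 weeks, assumed. Protocol 5.4 mentions 12 weeks only for most resolved second events.

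**Step 1. Any-time rule.** If seizure and ARIA are independent, the expected share of evaluable seizure participants shown with ARIA equals the any-ARIA incidence. For ARIA-E alone:

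- Low: 0.154 × 22% + 0.846 × 5% = 7.6%
- High: 0.154 × 22% + 0.846 × 17% = 17.8%
- With 35.4% in the naïve instead of 22%: 9.7% to 19.8%

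**Step 2. Adding ARIA-H.** The rate of ARIA-H without ARIA-E is not given. Across the Step 1 range (7.6% to 19.8%), an assumed 10 percentage points gives any-ARIA of 17.6% to 29.8%, and 19.1 points gives 26.7% to 38.9%. Phase 3 rates taken directly give between 35.4% (complete overlap of the three types) and 35.4 + 19.1 + 14.6 = 69.1% (none).

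**Step 3. Onset-within-episode rule, ARIA-E.** Chance share ≈ incidence × episode length / follow-up.

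| ARIA-E incidence | 12 of 170 weeks | 20 of 118 weeks |
|---|---|---|
| 7.6% | 0.5% | 1.3% |
| 17.8% | 1.3% | 3.0% |
| 35.4% | 2.5% | 6.0% |

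The reduction factor is follow-up / episode length, whatever the incidence: 118/20 = 5.9 to 170/12 = 14.2.

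**Step 4. Sensitivity of that factor**

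- Recurrence: Protocol 5.4 gives 236 participants with a second ARIA-E and 815 with a first, so about 1 + 236/815 = 1.29 episodes each, ignoring third and later ones. Factor: 5.9/1.29 = 4.6 to 14.2/1.29 = 11.0.
- Fixed 30-day (4.3-week) look-back: 118/(20 + 4.3) = 4.9 to 170/(12 + 4.3) = 10.4.
- Adding the whole interval since the previous scheduled MRI: 170/(12 + 8) = 8.5 with an 8-week gap, but 118/(20 + 24) = 2.7 with a 24-week gap.

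**Step 5. MRI spacing.** Protocol Table 4 schedules MRIs at screening, Weeks 14, 22, 30, 42, 54, 66, 78 and 102, then Week 170 for those completing the LTE. The longest gaps are 102 − 78 = 24 weeks in the core period and 170 − 102 = 68 weeks in the LTE as planned. The latter alone is 68/170 = 40% of planned follow-up.

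**The case against.** A reader might infer that a third or more of seizure participants will fall in the ARIA cell by chance. The documents do not support that. The 35.4% is the Phase 3 ARIA-E rate at the 10 mg/kg target dose, while about 85% of this study's pool had already been treated. Reaching one third from the 221AD103 rates needs a further 33.3 − 17.8 = 15.5 to 33.3 − 7.6 = 25.7 percentage points of ARIA-H without ARIA-E. For ARIA-E alone to reach it, the previously treated would need about (33.3 − 0.154 × 22)/0.846 = 35%. A third is possible, more so in the treatment-naïve, but not shown. The 221AD103 rates are uncertain in the other direction too: those participants continued treatment, whereas here dosing is re-titrated after a wash-out.

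The plan's other outputs also carry weight. A seizure attributed to ARIA appears in the ARIA-related AE table and carries the symptom flag. Seizures and the MRI assessments of participants with ARIA are listed, so a few cases can be read one by one. The SAP does not state the purpose of the seizure split, no testing is planned (SAP 5.1), and the study report is abbreviated. This is why the point is minor. It still stands: the attribution is an open-label investigator judgement, the listings leave date matching to the reader, and none of these outputs gives a date-based count.

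Finally, timing is not simple. ARIA starts at its detecting MRI, so with a fixed look-back a seizure during undetected ARIA could be filed as preceding ARIA. For ARIA-H, the end date means stability, not disappearance. Both objections stand, and the fix below allows for them.

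**Conclusion.** The point holds as a cheap improvement. The seizure split in SAP 5.7.4 ignores timing and pools ARIA-E with ARIA-H, so it contains a chance overlap equal to the any-ARIA incidence among evaluable participants. That incidence is not stated. ARIA-E alone contributes about 8% to 18% if the 221AD103 extension rates and the feeder-pool weights carry over, and more with ARIA-H or under Phase 3 rates.

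An onset-within-episode count would cut the ARIA-E part about 6- to 14-fold, or about 5- to 11-fold allowing for recurrence. This assumes independence, the planned follow-up and episodes of 12 to 20 weeks. The factor does not depend on which incidence is right. No comparable figure is offered for ARIA-H, because the documents give no usable episode length. The primary incidence summaries are unaffected.

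**What to change.** Keep the three cells in SAP 5.7.4. Subdivide the ARIA cell, once for ARIA-E and once for ARIA-H, by seizure onset:

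- (a1) within an ARIA episode dated by MRI as in SAP 5.7.3.1;
- (a2) between the last ARIA-free MRI and the detecting MRI, as its own row because the true ARIA onset is unknown there;
- (b) before the last ARIA-free MRI preceding the first ARIA;
- (c) after ARIA-E resolution or ARIA-H stabilisation, labelled so that stable is not read as resolved.

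Show the investigator's symptom-of-ARIA flag beside each row. Two definitions are needed. ARIA-free should mean without that new in-study finding, since exclusion criterion 4 lets previously treated participants enter with some micro-hemorrhages or siderosis. A participant with several seizures should be counted once, by a stated order such as a1, a2, c, b.

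The cost is a paragraph of SAP text and a date comparison on data already collected. There is no multiplicity cost, because nothing is tested. The downsides are small cells and imprecise ARIA onset where scheduled MRIs are sparse. Row a2 will be least informative in the LTE, so the table should footnote the MRI schedule.

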5.7.5. Clinical Laboratory Data

The following clinical laboratory parameters are assessed in the protocol and will be analyzed:

- 1. Hematology:
 - White blood cells (leukocytes), lymphocytes, neutrophils, monocytes, eosinophils, basophils
 - Red blood cells (erythrocytes), erythrocytes distribution width, erythrocytes mean corpuscular volume, erythrocytes mean corpuscular hemoglobin, erythrocytes mean corpuscular hemoglobin concentration
 - Hemoglobin
 - Hematocrit
 - Platelet count
- 2. Blood chemistry:
 - Liver: alanine aminotransferase (ALT), aspartate aminotransferase (AST), alkaline phosphatase (ALP), total bilirubin, direct bilirubin, gamma-glutamyl-transferase (GGT)
 - Renal: blood urea nitrogen (BUN), creatinine
 - Electrolytes: sodium, potassium, chloride, bicarbonate
 - Other: glucose, calcium, phosphorus, albumin, uric acid, lactate dehydrogenase (LDH), total protein
- 3. Urinalysis: specific gravity, potential of hydrogen (pH), color, blood, glucose, ketones, protein, white blood cells, red blood cells

²Haemorrhagic CNS vascular conditions event is defined by haemorrhagic central nervous system vascular conditions SMQ (broad and narrow scope).

³Hypersensitivity reaction event is defined by hypersensitivity SMQ (narrow and broad scope), angioedema SMQ (narrow and broad scope) and anaphylactic reaction SMQ (narrow and broad scope).

⁴Seizures event is defined by Convulsions SMQ (broad and narrow scope).

⁵Fall event is defined by the preferred Term "Fall".

Study: 221AD304 Version: 2.0

5.7.5.1. Quantitative analyses

For numeric laboratory parameters, actual values will be summarized by visit. Number of evaluable subjects, mean, standard deviation, median, 25% and 75% quartiles, minimum and maximum values will be presented at each visit.

Plots of mean actual values (with standard error) for numeric laboratory parameters at each visit will be provided.

Summary of change from 221AD304 baseline and percent change from 221AD304 baseline for numeric laboratory parameters will be presented at each visit. Number of evaluable subjects, mean, standard deviation, median, 25% and 75% quartiles, minimum and maximum values will be presented at each visit.

Visit windows for by visit summaries

For laboratory by visit summaries, the analysis visit should be defined using visit windows (see Table 7).

Analysis visit	Target visit day	Analysis visit window
221AD304 baseline	1	Last value prior to the first dose of aducanumab
Week 52	365	[2, 539]
Week 102	714	[540, 896]
Week 154	1078	>=897

5.7.5.2. Qualitative analyses

For qualitative analyses, all values will be included (not just the "analyzed record" within each visit window in the quantitative analyses).

Shift analyses

Laboratory data will be summarized using shift tables where appropriate. Each subject's hematology, blood chemistry and urinalysis numeric values will be flagged as "low", "normal", or "high" relative to the normal ranges of the central laboratory or as "unknown" if no result is available. Each subject's urinalysis categorical values will be flagged as "positive" or "negative", or "unknown" if no value is available.

Shifts from 221AD304 baseline to high/low status will be presented for hematology, blood chemistry and urinalysis numeric parameters, and shifts from 221AD304 baseline to abnormal (positive) will be presented for urinalysis categorical parameters. Shift to low includes normal to low, high to low, and unknown to low; Shift to high includes normal to high, low to high, and unknown to high. Subjects need to have at least one post-baseline evaluation and a baseline value not low or high or positive (including missing) to be included in the analysis.

Study: 221AD304 **Version:** 2.0

Potentially Clinically Significant laboratory abnormalities analyses

For hematology, blood chemistry and urinalysis, the number of subjects with potentially clinically significant laboratory abnormalities post-baseline will be summarized for the parameters provided in Table 8. Subjects need to have at least one post-baseline evaluation in the active treatment period and a baseline value not potentially clinically significant (including missing) to be included in the analysis.

Table 8 Criteria to Determine Potentially Clinically Significant (PCS) Laboratory
Abnormalities

Clinical Laboratory Abnormality Criteria		
Parameter name	PCS Low	PCS High
HEMATOLOGY		
White blood cells	<3.0 x 109/L	>16 x 109/L
Lymphocytes	<0.8 x 109/L	>12 x 109/L
Neutrophils	<1.5 x 109/L	>13.5 x 109/L
Monocytes	N/A	>2.5 x 109/L
Eosinophils	N/A	>1.6 x 109/L
Basophils	N/A	>1.6 x 109/L
Red blood cells	≤3.5 x 1012/L	≥6.4 x 1012/L
Hemoglobin - Females	≤95 g/L	≥175 g/L
Hemoglobin - Males	≤115 g/L	≥190 g/L
Hematocrit - Females	≤32%	≥54%
Hematocrit - Males	≤37%	≥60%
Platelet count	≤75 x 109/L	≥700 x 109/L
BLOOD CHEMISTRY		
Alanine aminotransferase (ALT)	N/A	>3 x ULN
Aspartate aminotransferase (AST)	N/A	>3 x ULN
Alkaline phosphatase (ALP)	N/A	>3 x ULN
Total bilirubin	N/A	>1.5 x ULN
Blood urea nitrogen (BUN)	N/A	≥10.7 mmol/L
Creatinine	N/A	≥176.8 umol/L
Sodium	≤126 mmol/L	≥156 mmol/L

Study: 221AD304 Version: 2.0

Clinical Laboratory Abnormality Criteria		
Parameter name	PCS Low	PCS High
Potassium	≤3 mmol/L	≥6 mmol/L
Chloride	≤90 mmol/L	≥118 mmol/L
Bicarbonate	≤16 mmol/L	≥35 mmol/L
Glucose	≤2.2 mmol/L	≥9.7 mmol/L
Calcium	≤2 mmol/L	≥3 mmol/L
Phosphorus	≤0.6 mmol/L	≥1.7 mmol/L
Albumin	≤25 g/L	≥625 g/L
Total protein	≤45 g/L	≥100 g/L
URINALYSIS		
Glucose	N/A	≥++++
Ketones	N/A	≥++++
Protein	N/A	≥++
ULN = upper limit of normal		

This table is from 221AD301 and 221AD302 study SAPs.

Potential serious hepatotoxicity

Potential serious hepatotoxicity is defined as ALT or AST ≥3x ULN and total bilirubin >2x ULN at any time post-baseline (not necessarily concurrent). A scatterplot of the maximum post-baseline ALT or AST value relative to ULN and maximum post-baseline total bilirubin value relative to ULN (not necessarily concurrent) for each subject will be provided. A line plot of ALT, AST, ALK and total bilirubin values over time for subjects with potential serious hepatotoxicity will be provided. A listing of subjects with potential serious hepatotoxicity will be provided.

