### 16.4.2.2. Clinical Laboratory Results

Laboratory data will be summarized using shift tables. Shifts from baseline to high/low status for hematology and blood chemistry parameters and shifts from baseline to high/positive status for urinalysis will be presented. In addition, the shift from baseline to the maximum postbaseline value and the shift from baseline to the minimum postbaseline status will be presented for each laboratory test. Also, summaries of laboratory values categorized based on common toxicity criteria grade will be created. Summary statistics for actual values and change from baseline will also be presented for quantitative laboratory data.

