5.10.2. Immunogenicity Analysis

Immunogenicity population will be used to analyze immunogenicity data. An immunogenicity summary table will be presented showing the number of subjects with anti-aducanumab antibody positive response at any time (including baseline), the number of subjects with treatment-emergent anti-aducanumab antibody positive response at each scheduled test visit, the number of subjects with transient positive response, and the number of subjects with persistent positive response. A listing of immunogenicity data for subjects with anti-aducanumab antibody positive results will also be provided. The immunogenicity summary table will be repeated for the core period.

Visit windows for by visit summaries

For immunogenicity by visit summaries, the analysis visit should be defined using visit windows (see Table 9 below).

Study: 221AD304 **Version:** 2.0

Table 9 Visit Windows for Immunogenicity by Visit Summaries

Analysis visit	Target visit day	Analysis visit window
221AD304 baseline	1	Last value prior to the first dose of aducanumab
Week 24	169	[2, 252]
Week 48	337	[253, 420]
Week 72	505	[421, 609]
Week 102	714	[609, 804]
Week 128	897	[805, 986]
Week 154	1078	>=987

6. Changes from Protocol-Specified Analyses

Table 10 lists the changes from protocol-specified analyses, including all analyses that are added, removed, and modified from those originally outlined in the protocol along with associated rationale/background for each change.

Table 10 Summary of Changes from Protocol-Specified Analyses

Protocol	SAP	Rationale/Background
	Excluded	
16.4.2.2. Clinical Laboratory Results Also, summaries of laboratory values categorized based on common toxicity criteria grade will be created	Excluded	CTCAE toxicity grade analyses are replaced with potential clinically significant (PCS) abnormality analyses.

Study: 221AD304 **Version:** 2.0

7. Summary of Changes from the Previous Version of the SAP

Due to early termination of the study, all displays will be presented by safety analysis groups (0 dose of BIIB037, 0 dose of 10 mg/kg, >0 dose of 10 mg/kg in feeder studies), or safety analysis groups stratified by laboratory

Analysis related to exposure/follow-up adjusted incidence rate, by previous exposure duration groups, and time-to-event analyses (Kaplan-Meier analysis) are excluded.

Table 11 provides details on the changes and reasons for changes from the previous version of the SAP.

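### The laboratory shift rule in SAP 5.7.5.2, read literally, excludes the subjects that two of its own six listed shifts require; the eligible baseline should be stated separately for each direction

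*SAP*

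**What the plan says.** SAP 5.7.5.2 (Shift analyses) classes each numeric laboratory result as low, normal, high or unknown, and each categorical urinalysis result as positive, negative or unknown. It then lists what is counted: "Shift to low includes normal to low, high to low, and unknown to low", and "Shift to high includes normal to high, low to high, and unknown to high". The next sentence sets eligibility: at least one post-baseline evaluation and "a baseline value not low or high or positive (including missing) to be included in the analysis". The same section says of post-baseline data that "For qualitative analyses, all values will be included", rather than one record per visit window.

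Protocol 16.4.2.2 asks for two things. The first is "Shifts from baseline to high/low status for hematology and blood chemistry parameters", with a matching display for urinalysis. The second is additional and applies to every test: "the shift from baseline to the maximum postbaseline value and the shift from baseline to the minimum postbaseline status will be presented". SAP 5.7.5 names no display of the second kind.

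SAP Section 6 describes Table 10 as covering the departures from the protocol, "including all analyses that are added, removed, and modified from those originally outlined in the protocol". Its only legible laboratory row records that "CTCAE toxicity grade analyses are replaced with potential clinically significant (PCS) abnormality analyses". Another row has no readable protocol entry, only the word Excluded. Table 11, on changes from SAP version 1.0, mentions only the CTCAE grade analysis among laboratory removals.

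**The concern.** The counting rule and the eligibility rule stand next to each other and cannot both be applied as written. A subject who is high at baseline is needed for a high-to-low shift but is not admitted, and the same holds for low-to-high. Two programmers could follow different sentences and produce tables with different counts and denominators, with nothing in the SAP to decide between them.

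This matters because the final analysis is a safety report and the shift table carries much of the categorical laboratory information. The CTCAE grade summaries have been removed. The potentially clinically significant (PCS) criteria in SAP Table 8 do not cover every test that SAP 5.7.5 says will be analysed: GGT, direct bilirubin, LDH, uric acid and the red-cell indices have no criterion there. For those tests the shift table is the only categorical display named in the legible text.

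**Working it through.** The plan gives no figure of its own to reproduce. The check is of a counting rule, followed by an illustration of size.

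**Step 1. Test each listed transition against the eligibility sentence.** Literal reading: baseline neither low nor high. Directional reading: baseline not low for shift to low, not high for shift to high.

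| Transition counted by the SAP | Literal | Directional |
|---|---|---|
| normal to low | possible | possible |
| high to low | impossible | possible |
| unknown to low | possible | possible |
| normal to high | possible | possible |
| low to high | impossible | possible |
| unknown to high | possible | possible |

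The literal reading leaves 4 of 6 transitions; the directional reading leaves all 6. Shift to positive is not in conflict, because the only baseline it needs to exclude is positive.

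**Step 2. Denominators.** Let L and H be the proportions low and high at baseline. The documents give neither, so the values below are assumptions. N = 1696 is the number enrolled (SAP 2.4). It is an upper bound, because the tables need a dosed subject with a post-baseline value.

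- Literal, both directions: N(1 − L − H)
- Directional: N(1 − L) for shift to low, N(1 − H) for shift to high

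| Assumed L / H | Literal, both | Directional, to low | Directional, to high |
|---|---|---|---|
| 2% / 5% | 1577 | 1662 | 1611 |
| 5% / 10% | 1442 | 1611 | 1526 |
| 10% / 20% | 1187 | 1526 | 1357 |

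For 5% / 10%, the shift-to-low denominator is 1 − 0.05 − 0.10 = 85% of subjects under the literal rule and 1 − 0.05 = 95% under the directional rule.

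**Step 3. Effect on the percentage shifting to low.** Let r be the shift rate among subjects with normal or unknown baseline, and q the rate among those high at baseline.

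- Literal percentage: r
- Directional percentage: [(1 − L − H)r + Hq] / (1 − L), which is (0.85r + 0.10q)/0.95 for 5% / 10%

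If q = 0, the ratio of literal to directional is 0.95/0.85 = 1.12. If q = r, the ratio is 1. If q exceeds r, it falls below 1. With L held at 5% and q = 0, the ratio is 0.95/0.90 = 1.06 for H = 5% and 0.95/0.75 = 1.27 for H = 20%. These ratios compare denominators; they carry over to the percentage only when no baseline-high subject shifts to low.

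**Step 4. The protocol's maximum and minimum shifts.** Because every post-baseline value is used, a subject has at least one high value exactly when the maximum is high, and at least one low value exactly when the minimum is low. Listing all 27 sequences of three post-baseline statuses (3 × 3 × 3) gave no mismatch. For eligible subjects, the SAP's shifts therefore already give the high and low content of the protocol's display. What is not planned is the full cross-table of baseline status by maximum and by minimum, for example high at baseline staying high or returning to normal.

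**The case against.** The strongest reply is that the eligibility phrase was never meant as one joint condition. It combines low and high, which apply to numeric tests, with positive, which applies only to categorical urinalysis, so it already has to be split by type of shift. Split fully, it agrees with the sentence before it and the conflict disappears. That is probably the intent, and a reader who infers that the plan is irreconcilable, or that opposite-direction shifts are certain to be zero, goes beyond the text. The reply does not settle the matter, though. Nothing says that the conditions apply respectively, no denominator is given by direction, and neighbouring rules use exclusions without direction: the PCS rule (5.7.5.2) requires a baseline that is not PCS at all, and the ECG rule (5.7.7) a baseline that is not abnormal. A programmer could reasonably follow the literal wording.

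A reader might also infer that the protocol's maximum and minimum shifts were dropped without record. The documents do not support that. Their high and low content survives for eligible subjects, and one Table 10 row cannot be read, so absence can be claimed only for the legible text.

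Nor does it follow that movement in baseline-abnormal subjects is invisible. Change from baseline by visit (5.7.5.1) has no such exclusion, and the hepatotoxicity plot and listing use post-baseline maxima for ALT or AST and bilirubin without one. A directional reading would itself show the opposite-direction shifts. It remains true that subjects staying high, or going from high to normal, appear in no named shift table.

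**Conclusion.** The eligibility sentence in SAP 5.7.5.2 is wrong as written. Taken literally, it empties two of the six transitions that the SAP says it counts and removes baseline-abnormal subjects from both denominators.

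The size cannot be fixed from the documents, because baseline-abnormal rates are not given. Under an assumed 5% low and 10% high, the shift-to-low denominator is 85% or 95% of subjects according to the reading. It would be a mistake to turn this into a general 12% inflation of the reported percentages, or a range of 1.06 to 1.27. Those factors assume that no baseline-high subject shifts to low; otherwise the percentages may agree or differ in the other direction.

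The consequence is confined to descriptive laboratory tables. SAP 5.1 plans no statistical testing, and laboratory shifts are not among the parameters listed under the core primary endpoints in SAP 2.1.1. The unnamed maximum and minimum cross-table is a secondary matter of traceability.

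**What to change.** Replace the eligibility sentence with:

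> A subject enters a shift analysis with at least one post-baseline result and, for shift to low, a baseline that is not low (normal, high or unknown); for shift to high, a baseline that is not high (normal, low or unknown); for shift to positive, a baseline that is not positive (negative or unknown). The denominator for each direction is the number of subjects eligible for that direction.

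Add a line to Table 10 recording that the protocol's full baseline-by-maximum and baseline-by-minimum cross-tables are not produced, and that their high and low content is given by the all-values shift analysis. Producing the cross-tables would also meet the protocol but is not necessary.

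The cost is one sentence and one table row. No new data are needed, and the tables planned stay the same.
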